4.4.7 Rescue Medication

Bisacodyl (Dulcolax®) 5 mg tablets will be supplied as rescue medication (RM) for the study. Patients will be instructed to take the study-provided rescue medication ONLY if 72 hours have elapsed since their last bowel movement. Therefore, patients should not take RM on more than two days per week. See Sections 3.3.2 and 6.2 for instructions on RM use.

5 STUDY CONDUCT

5.1 Schedule of Assessments

Ideally, the roll-over patient's participation in this trial begins as soon as participation in the core study SP304203-04 or SP304203-05 has ended.

For Core Study Completers, Day 1 / Baseline Visit of this study will commence after completion of the core study (End-of-Study visit - Visit 6).

For Eligible Screen Failure patients, the first visit of this trial will also ideally occur on the same day as the core study's Visit 2.

For patients that withdrew early from the core study due to lack of efficacy, the first visit of this trial will ideally occur on the same day as the core study's EW Visit.

The Schedule of Assessments for Core Study Completers or Eligible Screen Failure patients or patients that withdrew early who are enrolling on the same day or within 4 weeks of the last study drug dose or within 4 weeks of core study participation (Short Interval Patients) is presented in **Table 3**.

For (a) plecanatide study-naive patients, (b) SP304-20212 patients, and (c) Core Study Completers or Eligible Screen Failure patients when (i) more than 4 weeks elapsed since the patient's participation in the study or (ii) more than 4 weeks since the last study drug dose (Long Interval Patients), the patient will have to undergo additional assessments, specifically study participation begins with the Screening Visit (presented in **Table 4**).

Table 3: Schedule of Assessments for Short Interval Patients

Study Visit	Baseline Visit 1	Week 4 Visit 2	Week 12 Visit 3	Week 24 Visit 4	Week 36 Visit 5	Week 53 * (EOT) Visit 6	Early Withdrawal (EW)
Visit Day ± Visit Window	Day 1 ^(a)	Day 28 ± 4 days	Day 84 ± 7 days	Day 168 ± 7 days	Day 252 ± 7 days	Day 371 ± 7 days	Within 5 days of last study drug treatment
Informed Consent	X						
Rome IBS Modular Questionnaire ^b (Appendix 2)	X						
Inclusion/Exclusion Criteria	X						
Medical History (additional new information not recorded in the core study)	X						
Patient Questionnaires ^c		X	X	X	X	X	X
Concomitant Medications	X	X	X	X	X	X	X
Adverse Events	X	X	X	X	X	X	X
Physical Examination ^d		X	X	X	X	X	X
Vital Signs ^e		X	X	X	X	X	X
Pregnancy Test (urine) ^f	X	X	X	X	X	X	X
Urine Drug Screen	X						
Hematology, Serum Chemistry, Urinalysis ^g		X	X	X	X	X	X
Immunogenicity Testing ^h			X	X	X	X	X
12-lead ECG ⁱ				X		X	X
Study Drug Dispensation ^j	X	X	X	X	X		
Study Drug Collection ^k		X	X	X	X	X	X
Rescue Medication (RM) Dispensation ^l	X	X	X	X	X		

* EOT visit is for patients that either complete week 53 or complete due to sponsor termination of the study

- a. Ideally, Day 1 Visit will overlap with the end-of-study visit (Visit 6) of the core trial. The following most recent data collected at the core study: physical exam, vital signs, pregnancy test, ECG, labs (hematology, serum chemistry, urinalysis), immunogenicity testing, concomitant medications and adverse events will be used as baseline assessments in this study.
- b. Required for Screen-Failures, who do not have confirmation of active IBS-C done by diary in the core study.
- c. Selected questionnaires self-administered by patient, preferably prior to any other study assessments.
- d. PE will be based on the following body systems: general appearance, head (ear, eyes, nose, and throat), cardiovascular, respiratory, abdomen, musculoskeletal, neurological, lymph nodes, and skin.
- e. Seated blood pressure, heart rate, respiration, and temperature using the same calibrated instrument for each measurement.
- f. Urine pregnancy test performed on-site for women of childbearing potential (site must confirm negative result prior to proceeding).
- g. 6 to12 -hour fast is recommended before clinical laboratory assessments.
- h. Serum samples for immunogenicity testing for antibodies to plecanatide will be collected and stored until analysis. See Laboratory Manual for processing and shipping instructions.
- i. ECG is to be performed on the same calibrated machine during the study.
- j. The study drug will be dispensed at each visit as follows: one study drug kit on Day 1, two study drug kits at Week 4, three study drug kits at Week 12 and Week 24, four study drug kits at Week 36. Patient will take the Day 1 medication at the clinical site on Day 1; it is recommended that for dosing at home, patient will take study drug once daily at approximately the same time in the morning of each day.
- k. Patients will be instructed to return all unused study drug at the subsequent study visit. Site will perform study drug accountability at every visit.
- l. Rescue medication - Dulcolax tablets will be supplied (in commercial packaging) at the first study visit and re-supplied as needed throughout the study

Table 4: Schedule of Assessments for Long Interval Patients

Study Visit	Screening Visit 0	Baseline Visit 1	Week 4 Visit 2	Week 12 Visit 3	Week 24 Visit 4	Week 36 Visit 5	Week 53 (EOT) [*] Visit 6	Early Withdrawal (EW)
Visit Day ± Visit Window	Day -21 to -7**	Day 1	Day 28 ± 4 days	Day 84 ± 7 days	Day 168 ± 7 days	Day 252 ± 7 days	Day 371 + 7 days	Within 5 days of last study drug treatment
Informed Consent	X							
Rome IBS Modular Questionnaire (Appendix2) ^a	X							
Inclusion/Exclusion Criteria	X	X						
Medical History (additional new information not recorded in the core study)	X							
Patient Questionnaires ^b			X	X	X	X	X	X
Concomitant Medications	X	X	X	X	X	X	X	X
Adverse Events	X	X	X	X	X	X	X	X
Physical Examination ^c	X		X	X	X	X	X	X
Vital Signs ^d	X		X	X	X	X	X	X
Pregnancy Test (urine) ^e	X	X	X	X	X	X	X	X
Urine Drug Screen	X	X						
Hematology, Serum Chemistry, Urinalysis ^f	X		X	X	X	X	X	X
Immunogenicity Testing ^g		X	X	X	X	X	X	
12-lead ECG ^h	X			X			X	X
Study Drug Dispensation ⁱ		X	X	X	X	X		
Study Drug Collection ^j			X	X	X	X	X	X
Rescue Medication (RM) Dispensation ^k	X	X	X	X	X	X		

* EOT visit is for patients that either complete week 53 or complete due to sponsor termination of the study

** Minimum of 7 days should be allowed for plecanatide study-naïve and SP304-20212 patients between screening and baseline visits

- a. Rome IBS Questionnaire is required for Screen-Failure Patients who do not have confirmation of active IBS-C done by diary in study SP304203-04 or SP304203-05.
- b. Selected questionnaires self-administered by patient, preferably prior to any other study assessments.
- c. PE will be based on the following body systems: general appearance, head (ear, eyes, nose and throat), cardiovascular, respiratory, abdomen, musculoskeletal, neurological, lymph nodes, and skin.
- d. Seated blood pressure, heart rate, respiration, and temperature using the same calibrated instrument for each measurement.
- e. Urine pregnancy test performed on-site for women of childbearing potential (site must confirm negative result prior to proceeding).
- f. 6 to 12 hours fast is recommended before clinical laboratory assessments.
- g. Serum samples for immunogenicity testing for antibodies to plecanatide will be collected and stored until analysis. See Laboratory Manual for processing and shipping instructions.
- h. ECG is to be performed on the same calibrated machine during the study.
- i. The study drug will be dispensed at each visit as follows: one study drug kit on Day 1, two study drug kits at Week 4, three study drug kits at Week 12 and Week 24, four study drug kits at Week 36. . Patient will take the Day 1 medication at the clinical site on Day 1; it is recommended that for dosing at home, patient will take study drug once daily at approximately the same time in the morning of each day.
- j. Patients will be instructed to return all unused study drug at the subsequent study visit. Site will perform study drug accountability at every visit.
- k. Rescue medication - Dulcolax tablets will be supplied (in commercial packaging) at the first study visit and resupplied as needed throughout the study.

5.2 Procedures by Visit

Prior to initiating any study-related procedures, written informed consent must be completed and documented. When a patient is found to be eligible to enter the study, the investigator or designee will document enrollment of the patient in the site enrollment log. The Patient ID number will be the same as the 6-digit Patient ID used in the previous plecanatide study, except in rare circumstances when an administrative change to the Patient ID, pre-approved by the Sponsor, is required. The Patient ID number is also reflected as same in the eCRF.

Plecanatide study-naive and SP304-20212 patient numbering: A unique 6-digit patient number will be assigned consecutively for each patient using the site enrollment log selection after he or she signs the ICF. Unique patient numbers will begin with the clinical site number, e.g., 001 followed by a 3-digit number such as 601. The unique patient numbers will be assigned sequentially by clinical site personnel. For example, for clinical site number 002, the unique patient numbers might be as follows: 002-601, 002-602, 002-603, etc. The patient will keep this unique patient number for the duration of the study.

Depending on the length of time elapsed since participation in the core study (SP304203-04 or SP304203-05) and whether patient is plecanatide study-naive or from SP304-20212 patients are divided into two subgroups which will follow distinct initial enrollment requirements:

- 1) Patients who either completed the core study, withdrew early, or screen failed ≤4 weeks earlier (Study Completers, Early Withdrawals, and Eligible Screen Failures), will be enrolled into this study at the Baseline Visit, with study procedures described in section 5.2.2.1 (Short Interval Patients)
- 2) Patients, for whom more than 4 weeks elapsed since the core study participation (Study Completers, Early Withdrawals, and Eligible Screen Failures and plecanatide study-naive patients and SP304-20212 patients), will be enrolled into this study at the Screening Visit, with study procedures described in section 5.2.1 (Long Interval Patients)

Procedures at Weeks 4, 12, 24, 36, 53 and Early Withdrawal will be the same for all patients.

5.2.1 Screening Visit for plecanatide study-naive patients, SP304-20212 patients, and core study patients with enrollment delay of more than 4 weeks

This visit is required for plecanatide study-naive Patients, SP304-20212 patients and core study completers, eligible early withdrawals and eligible screen failures whose participation in the core study ended more than 4 weeks prior to enrollment into this study and for any patient needing a colonoscopy as per the guidelines in Appendix 3. For plecanatide study-naive and SP304-20212 patients only – the interval between screening and baseline visit must be at least 7 days.

The following procedures will be performed at this visit:

- Informed consent
- Rome IBS Modular Questionnaire (confirmation of IBS-C diagnosis via ROME III modular questionnaire (see Appendix 2) is required for patients not randomized in study SP304203-04 or SP304203-05.
- Review of inclusion/exclusion criteria
- Review of recent medical history (for information not already recorded in the core study)
- Review and recording of concomitant medications
- Physical examination

- Vital signs measurement
- 12-lead ECG
- Clinical laboratory assessments: hematology, serum chemistry, immunogenicity, urinalysis (see section 4.4.2 for details)
- Urine pregnancy test, if applicable
- Urine drug screen for selected opioids (see section 4.4.2 for details)
- Dispensation of study-provided rescue medication (Dulcolax®)

Patients who fail to qualify for enrollment into this study will be considered Screen Failures and the reason for failure will be documented. Once a patient screen fails in this study, they cannot be rescreened.

5.2.2 Baseline / Day 1 Visit

Patients who are Study Completers, Eligible Early Withdrawals, or Eligible Screen Failures and enrolling into this study within 4 weeks of the core study completion or within 4 weeks of the last study drug dose will begin with the Baseline / Day 1 Visit. The Baseline Visit assessments are described in section 5.2.2.1. Any adverse event that commenced during the core studies and are still ongoing/stable will be recorded on the Medical History CRF in SP304203-06, with the medical term and start date identical to those in the core study.

Adverse events that occurred during the core studies and resolved or ongoing prior to enrollment in SP304203-06 will be reported in SP304203-06 in the patient's medical history, according to their medical relevance.

Results of laboratory tests performed in the core study and used as baseline at Visit 1 of this trial must be evaluated within 72 hours of the visit to confirm the patient's continual eligibility for this open-label study.

5.2.2.1 Baseline Visit for patients enrolling on the same day or within 4 weeks of core study completion or screen-failure

Ideally, Day 1 / Baseline Visit of this study will commence immediately after completion of core study's end-of-study visit (Visit 6) for patients completing the study. For eligible SP304203-04 or SP304203-05 screen-failure patients, the first visit of this trial will also ideally occur on the same day as the core study's Visit 2. For eligible SP304203-04 or SP304203-05 early withdrawal patients, the first visit of this trial will also ideally occur on the same day as the core study's EW visit.

The following procedures will be performed on Day 1:

- Informed consent
- Rome IBS Modular Questionnaire (confirmation of IBS-C diagnosis via ROME III modular questionnaire (see Appendix 2) is required for patients not randomized in study SP304203-04 or SP304203-05.
- Review inclusion/exclusion criteria
- Pregnancy Test (urine)
- Urine Drug Screen
- Review and recording of concomitant medications and procedures (only for new information that is not recorded in the core study)
- Medical History (new information that is not recorded in the core study must be captured in the source documents and eCRF)
- Dispensation of study drug

- Dispensation of study-provided rescue medication (RM)

If the SP304203-06 baseline visit is within 4 weeks of the end-of-study visit (Visit 6) of the core study, certain data collected at Visit 6 or Visit 5 or Visit 2 of the core study will also be used as the data for the SP304203-06 baseline visit, i.e., these assessments do not have to be performed again for entry into SP304203-06, for practical reasons. This is indicated in the Schedule of Assessments in **Table 3**.

The following last set of results collected at the core study (at Visit 5) will be used as baseline assessments in this study:

- Physical exam
- Vital signs
- Laboratory tests (hematology, serum chemistry, urinalysis)
- ECG
- Immunogenicity testing
- Medical History (new information that is not recorded in the core study must be captured in the source documents and eCRF)
- Review and recording of concomitant medications and procedures (new information that is not recorded in the core study must be captured in the source documents and eCRF)
- Review and recording of adverse events (new information that is not recorded in the core study must be captured in the source documents and eCRF)

5.2.2.2 Baseline Visit for plecanatide study-naïve patients, SP304-20212 patients, and patients enrolling after more than 4 weeks of core study participation

For patients enrolling more than 4 weeks after the core study participation, plecanatide study-naïve patients, and SP304-20212 patients and who completed the Screening Visit of this study, the following assessments will be performed at the Baseline Visit:

- Review inclusion/exclusion criteria
- Review and recording of concomitant medications
- Review of adverse events
- Pregnancy Test (urine)
- Urine Drug Screen
- Immunogenicity sample collection
- Dispensation of study drug
- Dispensation of study-provided rescue medication (RM)

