4 VARIABLES AND METHODS OF ASSESSMENT

4.1 Demographics and Baseline Characteristics

Demographic data, medical history (including ongoing AEs) and previous/concomitant medications recorded in the eCRF of the previous plecanatide core study will be replicated in the eCRF for this open-label study when the patient signs the informed consent and is enrolled into this open-label study. New information or clinically-significant changes since the core trial will be solicited from all patients for appropriate updates to the eCRF for this open-label study.

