4.4 Safety Variables

4.4.1 Collection of Adverse Events

Adverse event (AE) collection for the study will begin immediately after the ICF is signed. All AEs occurring prior to first dose of study drug are considered medical history (MH). It is the responsibility of the Investigator to ensure that all serious and non-serious AEs are collected. For details on the assessment, reporting, recording and follow-up of adverse events, see Section 7. IBS-C is characterized primarily by abdominal pain and constipation; however, several additional symptoms are often associated with IBS-C including abdominal discomfort, abdominal bloating, incomplete evacuation and straining with bowel movements. Because IBS-C is the condition under study in this clinical trial these IBS-C related symptoms are expected over the course of a patients participation in the trial; therefore, when reported as related to IBS-C, these symptoms should not be recorded as adverse events.

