- Urine pregnancy test for women of childbearing potential
- Clinical laboratory assessments
- Immunogenicity sample collection
- 12-lead ECG
- Study drug collection and accountability

In all cases, the reason(s) for withdrawal, and the primary reason, must be recorded on the eCRF and source records. If the primary reason for withdrawal is an adverse event, a single adverse event must be recorded as the primary reason. Patients who prematurely withdraw from study treatment will not be eligible to participate in this or any other plecanatide study in the future. Patients withdrawn after enrollment into the study will not be replaced.

For patients lost to follow-up, every attempt of contact (i.e. phone calls and registered letters) must be documented in the patient's source records.

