7 ASSESSMENT, REPORTING, RECORDING AND FOLLOW UP ADVERSE EVENTS

7.1 Definitions

An AE is any untoward medical occurrence associated with the use of a drug in humans, whether or not considered drug-related. An AE can therefore be any unfavorable and unintended sign (including abnormal laboratory finding), symptom, or disease temporally associated with the use of an investigational product or study procedure whether or not considered related to the product or procedure. All AEs, including intercurrent illnesses and regardless of the source of identification (e.g., PE, laboratory assessment, ECG, reported by patient), occurring during the study will be documented in the eCRF. Concomitant illnesses, which existed before entry into the study, will not be considered AEs unless they worsen (increase in intensity or frequency) during the treatment period.

Adverse events occurring from the time of ICF signing up to the intake of the first dose of study drug will be classified as pre-existing conditions for this study. Serious AEs (as defined below) occurring from the time of ICF signing up to the intake of the first dose of study medication will be collected and reported as such. A TEAE is defined as an AE that begins or that worsens in frequency and/or severity after at least one dose of study drug has been administered.

Minor fluctuations in laboratory values for standard monitoring (abnormal values) that the Investigator does not consider clinically significant or related to study drug will not be recorded as AEs. However, if the laboratory abnormality is associated with a diagnosis, then the AE term for that diagnosis will be reported (see Section 7.4 for recording of AEs).

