8.9 Safety Analyses

Evaluation of the safety of once daily (QD) plecanatide over 53 weeks of dosing will be based on the occurrence of TEAEs, vital signs, clinical laboratory assessments, physical examinations and ECGs as recorded in the clinical database. The safety analyses will use the Safety Population defined in Section 8.3.

Adverse events will be coded using Medical Dictionary for Regulatory Activities (MedDRA) classifications with reference to system organ class and preferred terms. While all AEs will be listed, only TEAEs will be included in summary tables. Summaries of TEAEs will be presented by system organ class and preferred term. Tabular summaries will include frequency of TEAEs overall and by intensity and by relationship to study drug. Incidence rates by person-time will also be presented. TEAEs leading to treatment interruption, withdrawal from treatment, and SAEs will be presented separately.

Out of range laboratory tests, ECGs and vital signs of potential clinical importance will also be summarized. A listing of patients with at least 1 out of range value will be presented by visit for that test.

Hematology, serum chemistry, and urinalysis absolute values and, where applicable, changes from baseline for each of the laboratory assessments will be presented over time. An additional listing will be produced of clinically significant laboratory parameters. Shift tables will also be produced.

Changes in vital signs and ECG evaluations will be presented. Absolute values and changes from baseline for each parameter will be presented, where applicable.

Concomitant medications will be auto-encoded using the World Health Organization Drug Dictionary (WHODD) coding system with reference to Anatomical Therapeutic Chemical (ATC) Classification System text and preferred terms. Summaries of concomitant medication will be presented by ATC text and preferred terms. Prior and concomitant medications will be presented separately.

All physical examination findings will be presented in the data listing.

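### Core-study AEs still ongoing at entry become medical history, so unless they worsen, their persistence and any resulting interruption or withdrawal are not tabulated, and AE-free days are left undefined

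*Combined protocol and SAP*

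**What the plan says.** Section 5.2.2 states: "Any adverse event that commenced during the core studies and are still ongoing/stable will be recorded on the Medical History CRF in SP304203-06", keeping the core-study term and start date. The paragraph that follows says that core-study events which resolved or were ongoing before enrollment "will be reported in SP304203-06 in the patient's medical history, according to their medical relevance". Section 4.1 points the same way: "Demographic data, medical history (including ongoing AEs) and previous/concomitant medications recorded in the eCRF of the previous plecanatide core study will be replicated" in this study's eCRF. Section 4.4.1 classes AEs arising before the first dose as medical history.

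Section 7.1 says that illnesses present before entry "will not be considered AEs unless they worsen (increase in intensity or frequency) during the treatment period", and adds: "A TEAE is defined as an AE that begins or that worsens in frequency and/or severity after at least one dose of study drug". Section 8.9 states: "While all AEs will be listed, only TEAEs will be included in summary tables". It then presents separately the TEAEs that led to interruption or withdrawal.

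Three other places matter:
- Section 8.6.1 plans a descriptive baseline summary of medical history and names ongoing AEs from the earlier trial as part of it.
- Section 5.2.5 requires: "If the primary reason for withdrawal is an adverse event, a single adverse event must be recorded as the primary reason".
- Sections 2.4.1 and 8.8 name AE-free days, and interruptions caused by diarrhea or another AE, as tolerability measures. Section 8.8 leaves the detail to the SAP. The document supplied contains no SAP text and no definition of an AE-free day.

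**The concern.** Sections 1, 3 and 5.2.2 prefer roll-over on the day the core study ends. A patient from a plecanatide arm may then move from one study to the next with little or no break in treatment. Inclusion criterion 1 bars completers who had a drug-related SAE. It does not bar those with an ongoing non-serious related event, although Section 3.2 allows exclusion for a significant decline in health or on medical judgment.

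The primary objective is long-term safety and tolerability. Whether an early side effect persists, resolves or eventually makes the patient stop is central to that objective. For events carried over unchanged, the planned tables answer none of these questions. Interruptions and withdrawals due to AEs are named endpoints in Section 2.4.1, so uncertainty about how to record them reaches the endpoints directly.

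**Working it through.** There is no stated figure to reproduce: the study is single-arm and descriptive, and Section 8.2 says power calculations do not apply. The check is mainly a reading of the rules in sequence.

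**Tracing one event.** Take a non-serious AE that began on plecanatide in a core study, in a patient who rolls over the same day with the event unchanged.
1. Section 5.2.2: it goes on the Medical History CRF with its term and start date. No end date or action taken with study drug is called for there. Section 7.4 requires those items, and Section 7.6 requires follow-up to resolution, but both sections concern AEs.
2. Section 7.1: it neither begins nor worsens after the first dose here, so it is not a TEAE.
3. Section 8.9: it enters no TEAE incidence or person-time table, and no table of TEAEs leading to interruption or withdrawal.
4. Section 8.6.1: it is counted once, at baseline. Section 8.4 summarizes by open-label treatment, which is a single group, so onset on plecanatide is not separated from onset on placebo.
5. Section 5.2.5: if the patient leaves because of it, a single AE must be named, yet no AE record need exist in this study. A site could name the medical-history event, give another reason, or open a new AE with a new start date. The protocol does not say which.
6. Section 8.8: nothing says whether days with the event are AE-free. If the measure means days without a recorded AE, they would be.

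**The two sentences of Section 5.2.2.** One records any ongoing AE. The other covers ongoing AEs too but makes reporting depend on medical relevance. A site cannot be sure which governs.

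**Illustration of size.** Document inputs: 9.3% diarrhea at 3.0 mg over 12 weeks in the IBS-C phase 2 study (Section 2.1.3), 371 days of participation (Section 9.9; 53 × 7 = 371) and about 1500 patients (Section 8.1). Assumption: a share *f* of diarrhea cases is ongoing and unchanged at roll-over.

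Missing incidence among roll-overs from plecanatide arms = 9.3% × *f*. Overstatement of mean AE-free days per such patient, if the event's days were counted as AE-free = duration × 0.093 × *f*.

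| *f* | Missing incidence | Cases per 1000 | Days, if all 371 affected | Days, if 28 affected |
|---|---|---|---|---|
| 5% | 0.465% | 4.65 | 1.7 | 0.13 |
| 10% | 0.93% | 9.3 | 3.5 | 0.26 |
| 25% | 2.325% | 23.25 | 8.6 | 0.65 |
| 50% | 4.65% | 46.5 | 17.3 | 1.30 |

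For the whole study, let *g* be the assumed share of enrollment from plecanatide arms. Cases = 1500 × *g* × 0.093 × *f*:
- *g* = 25%, *f* = 5%: 1.7.
- *g* = 75%, *f* = 50%: 52.3.

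Some patients with diarrhea will have withdrawn and not rolled over. Subtracting the 3% who withdrew for diarrhea at 3.0 mg in the CIC phase 2b study (a different population) leaves 6.3%. Every figure then falls by about a third (0.063/0.093 = 0.68).

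**The case against.** The case on the other side is substantial.

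- **The events are not lost.** Section 8.6.1 summarizes them, Section 4.1 replicates them, and Section 5.2 generally keeps the same patient number, so linkage to core-study data is possible. A reader might infer that these patients are recorded as having no event; that is wrong. What stands is that a baseline count shows presence, not persistence, resolution or consequence.
- **Worsening is covered.** An increase in frequency or severity makes the event a TEAE, and an event that newly forces a patient to stop may often qualify. What stands is the event that stays the same and is eventually not tolerated.
- **The tolerability measures are wider than TEAEs.** Section 2.4.1 speaks of withdrawals and interruptions due to AEs, and Section 5.2.5 records the reason for withdrawal. A carried-over cause may therefore be captured. But Section 8.9 builds its interruption and withdrawal presentation on TEAEs, and no rule connects the two.
- **Keeping these events out of the TEAE tables is conventional.** For events that began on placebo it is also correct. This stands, and it is why the TEAE definition need not change.
- **The conflict in Section 5.2.2 may be only loose drafting.** The first sentence is mandatory, and Section 4.1 supports it. This is a fair reading, but the text leaves sites to choose it.

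**Conclusion.** The point holds in limited form. A stated rule keeps unchanged core-study AEs out of this study's TEAE tables and its TEAE-based interruption and withdrawal presentation, even when they began on plecanatide and treatment continued without a break. Their persistence and consequences are not otherwise summarized. AE-free days lack a definition, and Section 5.2.2 is inconsistent.

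Two stronger readings are not supported. A reader might infer that days with a carried-over event do count as AE-free; the documents leave this open, and the firm finding is the missing definition. A reader might also infer that the rule always favors tolerability. It covers placebo-onset events as well, which are rightly not TEAEs here, and site coding of withdrawals may differ in either direction.

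The true size cannot be determined: neither the share of events ongoing at roll-over nor the share of patients from plecanatide arms is given. On the assumptions shown, diarrhea alone gives about 2 to 52 patients in 1500. The upper end needs half of all cases to be ongoing and three quarters of enrollment to come from plecanatide arms. The 9.3% comes from 3.0 mg, whereas this study gives 6 mg. The 371-day column is a ceiling. The effect is probably modest, but the correction is cheap and worth making.

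**What to change.** **Section 5.2.2.** Reconcile the two sentences so that every AE ongoing on Day 1 is recorded with its original term and start date, a flag for *ongoing at entry*, an end date and the action taken with study drug.

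**Sections 8.8 and 8.9, carried into the SAP.**
- Define an AE-free day, and count days with a flagged event as not AE-free.
- Include flagged events in the interruption and withdrawal tables, identified as carried over, so that the reason required by Section 5.2.5 has a matching record.
- Add one table of flagged events by core treatment received, with time to resolution, beside the TEAE table.

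Leave the TEAE definition unchanged. No clinical rule is affected.

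The cost is a few added eCRF fields rather than a flag alone, because time to resolution needs an end date that Section 5.2.2 does not now call for. There is also one extra table, and the tolerability figures may look slightly less favorable.
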